Appendix 3 Haemophilia Joint Health Score

Hemophilia Joint Health Score 2.1 - Summary Score Sheet

	Left Elbow	Right Elbow	Left Knee	Right Knee	Left Ankle	Right Ankle
Swelling	□ NE	□NE	□ NE	□NE	□ NE	□NE
Duration (swelling)	□ NE	□ NE	□ NE	□ NE	□ NE	□ NE
Muscle Atrophy	□ NE	□NE	☐ NE	□ NE	□ NE	□ NE
Crepitus on motion	□ NE	□NE	□ NE	□NE	□NE	□ NE
Flexion loss	□NE	□ NE	□ NE	□ NE	□ NE	□ NE
Extension loss	□ NE	□NE	□ NE	□NE	□ NE	□ NE
Joint pain	□ NE	□NE	□NE	□NE	□ NE	□ NE
Strength	□ NE	□ NE	□ NE	□NE	□ NE	□ NE
Joint Total						

[figure not shown]
Extension loss	□ NE								
	tool EVIC	□ NE	□ NE	□ NE	□ NE	□ NE			
Joint pain	□ NE	□NE	□NE	□NE	□ NE	□ NE			
Strength	□ NE	□NE	□NE	□NE	□ NE	□ NE			
Joint Total					1	1.0			
Joint Total						-			
Sum of Joint Totals	• 🛨 🗀			0)	NE = Non-Evalua	ible			
Global Gait Score									
	(□ NE in	cluded in Gait ite	ms)						
HJHS Total Score									
Swelling	Crepitus on M	Motion	Strength (Us	ing The Daniels	& Worthinghan	n's scale)			
) = None	0 = None		Within available						
1 = Mild	1 = Mild				ty within maximum r				
2 = Moderate 3 = Severe	2 = Severe		Holds test position against gravity within moderate resistance (but breaks with maximal resistance) (gr. 4) Holds test experimental resistance) (gr. 4)						
	Flexion Loss		2 = Holds test position with minimal resistance (gr. 3+) or holds test position against gravity (gr. 3)						
Duration	0 = < 5°		3 = Able to partially complete ROM against gravity (gr.3-/2+)						
0 = No swelling	1 = 5° - 10°		5.25 All 11 (1988)	이 그 그 것도 되었다면 살아왔다면 아이에 가장 그렇게 하면 하면 하면 보고 있다면 하다고 하고 있다면 하다 하는데 없다면 하는데 없다면 하다 하는데 없다면 하					
Or < 6 months	2 = 11° - 20°		Or able to move through ROM gravity eliminated (gr. 2) Or through partial ROM gravity eliminated (gr. 2-)						
1 = ≥ 6 months	3 = > 20"			or no muscle contra					
S CONTRACTOR .			NE = Non-Evaluable						
Muscle Atrophy	Extension Lo	SS							
) = None	(from hyperextens	sion)	Global Gate						
1 = Mild	0 = < 5*		0 = All skills are within normal limits 1 = One skill is not within normal limits 2 = Two skills are not within normal limits						
2 = Severe	1 = 5° - 10°								
	2 = 11° - 20°								
actions to serve	3 = > 20°			are not within norma					
Joint Pain			4 = No skills are	within normal limits					
0 = No pain through active r 1 = No pain through active r gentle overpressure or p	range; only pain on palpation		NE = Non-Eva	luable					
2 = Pain through active rang									
2 = Pain through active rang	mpanying instruct	ion manual an	d worksheets tha	t are required wi	nen administerin	g the HJH			

Appendix 4 European Quality of Life-5 Dimensions (EQ-5D-5L)

Under each heading, please tick the ONE box that best describes your health TODAY. MOBILITY I have no problems in walking about I have slight problems in walking about I have moderate problems in walking about I have severe problems in walking about I am unable to walk about SELF-CARE I have no problems washing or dressing myself I have slight problems washing or dressing myself I have moderate problems washing or dressing myself I have severe problems washing or dressing myself I am unable to wash or dress myself USUAL ACTIVITIES (e.g. work, study, housework, family or leisure activities) I have no problems doing my usual activities I have slight problems doing my usual activities I have moderate problems doing my usual activities I have severe problems doing my usual activities I am unable to do my usual activities PAIN / DISCOMFORT I have no pain or discomfort I have slight pain or discomfort I have moderate pain or discomfort I have severe pain or discomfort I have extreme pain or discomfort ANXIETY / DEPRESSION I am not anxious or depressed I am slightly anxious or depressed I am moderately anxious or depressed I am severely anxious or depressed I am extremely anxious or depressed

- · We would like to know how good or bad your health is TODAY.
- . This scale is numbered from 0 to 100.
- 100 means the best health you can imagine.
 0 means the worst health you can imagine.
- . Mark an X on the scale to indicate how your health is TODAY.
- Now, please write the number you marked on the scale in the box below.

YOUR HEALTH TODAY =

Appendix 5 Device compatible with the ePRO application and with the fitness tracker (Fitbit Versa model)

ANDROID DEVICES

Coolpad									
F2	^								
Google									
Pixel 3	Pixel	Nexus 6							
Pixel 3 XL	Pixel XL	Nexus 5x							
Pixel 2	Nexus 9	Pixel 2 XL							
Nexus 6p									
нтс									
One M9	One M8	One E8							
Desire 516*	One Mini 2	Desire 816							
Desire 610									
	Huawei								
P20 Pro	P20 Lite	P10							
Honor 8	Honor 6X	Honor 6							
Honor 6 Plus	Mate 9	Ascend P7							
Ascend P8									
	Lenovo								
Vibe Z2 Pro	Vibe X2								
	LG								
V10	G6	G3							
G2	G Pro2								
	Motorola								
Moto E (2015)	Moto E (2014)	Moto G (2014)							
Droid Turbo	Droid Turbo 2	Moto Z							
X4	G5S								
	OnePlus								
OnePlus One	OnePlus 6								
	Samsung								
Galaxy S9	Galaxy S9+	Galaxy S8							
Galaxy S8+	Galaxy A8	Galaxy S7							
Galaxy S7 Edge	Galaxy S7 Edge Plus	Galaxy S6							
Galaxy S6 Edge	Galaxy S6 Active	Galaxy A6							
Galaxy S5	Galaxy S5 Active	Galaxy S5 Sport							
Galaxy S4	Galaxy S4 mini	Galaxy S4 Active							
Galaxy S3 Neo	Galaxy Note 3 Neo	Galaxy Ace Style							
Galaxy Note Pro	Galaxy J3	Galaxy Alpha							
Galaxy Note 9									
	Sony								
Xperia XZ2	Xperia Z3	Compact							
Xperia Z3 Dual	Xperia Z2 Ultra	Xperia Z2							

Xperia Z1	Xperia Z1 Compact	Xperia ZL				
Xperia XA	Xperia T2 Ultra	Xperia M2				
Xperia E1						
Xiaomi						
Mi4	Red Mi 2					
ZTE						
Nubia Z7 Max						

^{**} if Android > 4.4

IOS DEVICES

iPhone XS Max	iPhone 6S	iPad Mini 3rd gen
iPhone XS	iPhone 6 Plus	iPad Mini 2nd gen
iPhone XR	iPhone 6	iPad 4th gen
iPhone X	iPhone SE	iPad Air 2
iPhone 8 Plus	iPhone 5S	iPod Touch 6th gen
iPhone 8	iPhone 5c	iPhone 7
iPhone 7 Plus	iPhone 5	iPhone SE
iPhone 6S Plus	iPad Pro 12.9"	iPad Mini 4th gen
iPad Pro 9.7"

## **STATISTICAL ANALYSIS PLAN AMENDMENT RATIONALE**

### **Amendment 1.1: 02 February 2022:**

All the co-primary endpoints presented in Section 2.2.1, i.e.:

- active minutes:
  - heart zone minutes (overall, fat-burn minutes, cardio minutes, peak minutes)
  - active zone minutes (overall, lightly active minutes, fairly active minutes, very active minutes)
  - MVPA minutes
- METs
- number of steps

will be summarized at subject level as median per day (i.e. the median of each parameter will be calculated by using all the valid days collected during the observational period). In this way it is possible to obtain a more robust measurement that is not affected by the presence of outliers related to scattered peak of physical activity or errors in the measurement related to the fitness tracker.

### **Amendment 1.2: 08 June 2022:**

The changes done in this amendment mainly regard the definition of the evaluable population. The following section have been changed:

- Section 4.1.2: the definition of the Evaluable population has been updated by including a condition on the compliance to the use of the fitness tracker in addition to the presence of a valid period defined by an exposure of at least 180 days (6 months)
- Section 4.3.2.1: a definition of the compliance to the use of fitness tracker relatively to the period defined by the extent of exposure (from the first valid day to the last valid day, extremes included) has been added.

Moreover, the following sentence has been added in Section 4.0:

*With reference to the ePROs and physical activity data (i.e. all data derived from ePRO app and the fitness tracker), only data collected between the informed consent date and Date of patient completion or withdrawal (extremes included) will be analyzed. For the interim analysis, the minimum between Date of patient completion or withdrawal and the cut-off date will be considered as upper bound.*

### **Amendment 2.0: 15 July 2022:**

In section 2.2.1 the types of physical activities identified by the fitness tracker have been listed.

In Section 4.1.4, the definition of SWITCH population has been added along with the classification of subjects who switch to a replacement or non-replacement therapy.

In Section 4.2.3, the time to discontinuation will be analyzed even if less than 30% of subjects will discontinue the study in order to provide an estimate of the median follow-up time.

In Section 4.4.2, the following changes have been done:

- Treatment regimen for bleeding: number and proportion of bleeding with adherence to treatment regimen in the week preceding the bleeding will be shown.
- HRQoL measured using the EQ-5D-5L will be analyzed monthly instead of every 3 months, deriving the timepoint from the date in which the questionnaire is recorded in the ePRO.
- Annualized Bleeding Rate: Number and proportion of subjects with at least one bleeding will be also shown.
- The analysis to explore the relationship between bleedings and physical activity has been explained better.

In Section 4.4.4, the following changes have been done:

- the definition of subgroups accordingly to the start of any newly approved drug for haemophilia has been updated.
- the analysis by month to observe the impact of COVID-19 has been added.

## 1. BACKGROUND

This document outlines the statistical methods to be implemented in the analysis of the data of ML40983 Clinical Study. The purpose of this plan is to provide general guidelines from which the analysis will proceed, containing a more technical and detailed elaboration of the principal features of the analysis described in the protocol. Any changes to the protocol (1) or electronic Case Report Form (eCRF) (2) may necessitate updates to the Statistical Analysis Plan (SAP). In case of deviations from this updated SAP, explanations will be provided in the clinical study report.

All final study data will be considered for the analysis regulated by this SAP.

## 2. STUDY DESIGN

This is a multicenter, non-interventional, prospective study. The study will be conducted according to the scheme shown in Table 1 and includes two phases: baseline and observational period.

This study will include patients aged  $\geq 12$  years and  $\leq 50$  years with severe ( $\text{FVIII} < 1\%$ ) or moderate ( $\text{FVIII} \geq 1$  and  $\leq 2\%$ , i.e., in the higher range of severity) Haemophilia A without inhibitors against FVIII.

**Table 1: Study scheme**

		Observational period	
		Standard observational period for all observed patients	Prolonged observational period if patients start newly approved drugs between Month 6 and Month 12
Baseline	Month 0 to Month 12	6 months after the start of new therapy (e.g., max observation period of 18 months if patients start the newly approved drugs during the last month of standard observational period).	

The entire observational period will last 12 months. Patients that will start treatment with any newly approved drugs between Month 6 and Month 12 will complete a 6-month observational period after the switch, and therefore the entire observational period in these patients may be prolonged up to a maximum of 18 months. In the context of this study, newly approved drugs are considered all those newly approved

during the study and commercially available for prophylaxis treatment in patients with Haemophilia A without inhibitors.

## 2.1 PROTOCOL SYNOPSIS

The Protocol Synopsis is in Appendix 1.

For additional details on the Visit Schedule and Visit Windows, see the Schedule of Assessments in Appendix 2.

## 2.2 OUTCOME MEASURES

The co-primary outcome measures are given by the physical activity data collected through a wearable device (i.e., fitness tracker) in terms of active minute, METs and steps count.

According to the protocol (see Study protocol, Section 6.1.1), a valid day of monitoring is defined as at least 10 wearing hours per day. Only data from days in which the fitness tracker was worn for at least 10 hours will be included in the statistical analysis (see Appendix 3 for the derivation of the wearing time).

The minutes are saved in two different sets of data collected by the fitness tracker. For each set, minutes are categorized by intensity of the activity done.

The first set is comprised of the minutes categorized accordingly to the time collected in each heart zones (following referred as “heart zone minutes”):

- fat-burn minutes,
- cardio minutes,
- peak minutes.

The second set is comprised of the minutes categorized accordingly to the active zones (following referred as “active zone minutes”):

- lightly active minutes,
- fairly active minutes,
- very active minutes.

The conversion from heart zones to active zones is not shared by the owner of the fitness tracker but it is known that it is based on the METs (Metabolic Equivalent of Task). The MET is the objective measure of the ratio of the rate at which a person expends energy, relative to the mass of that person, while performing some specific physical activity compared to a reference. METs calculated by the fitness tracker are not directly available but must be derived.

In our analysis, the METs will be derived by using the following formula:

$$1 \text{ MET} = \frac{\text{kcal}}{\text{kg} * \text{h}}$$

where:

- $kcal$  will be given by the sum of calories collected by the fitness tracker during the time spent in fat-burn, cardio and peak heart zones, respectively.
- $kg$  will be given by the weight collected in the eCRF at baseline and every 3 months when the observation visit is conducted and the weigh is collected (the weight is assumed constant between each visit and the subsequent, in case of missing assessment, the last available value will be carried forward).
- $h$  is the time that will be derived as sum of fat-burn minutes, cardio minutes, and peak minutes.

The minutes will be also analyzed in terms of overall sum:

$$\begin{aligned} \text{overall heart zone minutes} &= \\ &= \text{fatburn minutes} + \text{cardio minutes} + \text{peak minutes} \end{aligned}$$

$$\begin{aligned} \text{overall active minutes} &= \\ &= \text{lightly active minutes} + \text{fairly active minutes} + \text{very active minutes} \end{aligned}$$

And of MVPA (Moderate-to-Vigorous Physical Activity) minutes:

$$\text{MVPA minutes} = \text{fairly active minutes} + \text{very active minutes}$$

### 2.2.1 Secondary Endpoints

- To document physical activity, particularly in terms of active minutes, by ages categories (12-17, 18-30 and 31-50 years), by type of physical activity and by intensity (as per fitness tracker default categorization)
  - The physical activities are categorized in the followings groups:
    - Exercises at intervals
    - Gymweights
    - Running
    - Swimming
    - Tapis roulant
    - Walk
    - General exercises: other types of physical activity identified by the fitness tracker that are not already included in the above-mentioned categories.
- To describe the observed population in terms of:
  - Number of patients who are adherent to World Health Organization (WHO) Guidelines (i.e., Global Recommendations on Physical Activity for Health) for the definition of physical activity.

The adherence to WHO guidelines will be derived considering the measures derived as described in Section 4.1.

A patient will be defined “adherent” to WHO guidelines if:

- 12-17 years old:

- MVPA minutes per day  $\geq$  60 minutes
- 18-50 years old:
  - Fairly active (moderate) minutes per week  $\geq$  150 minutes OR
  - Very active (vigorous) minutes per week  $\geq$  75 minutes OR
  - An equivalent combination of fairly and very active minutes (i.e. considering 1 fairly active minute as 0.5 very active minutes)

A subgroup analysis will be done by severity of the disease (see Section 4.4.5 for subgroup definition).

A patient who will result adherent to the WHO guidelines according to the previous definition will be define as an “active patient”, otherwise as a “sedentary patient”.

- Number, sites and types of bleeds occurring during routine clinical practice and reported at any occurrence via the electronic Patient-Reported Outcome (ePRO) application.
- Treatment regimen for haemophilia A (prophylaxis, preventative treatment before physical activity, treatment for any episode of bleeds), in terms of type of regimen (on demand vs. prophylaxis), product used and dose.
- Health-Related Quality of Life (HRQoL) and health status reported during routine clinical practice, measured using the European Quality of Life-5 Dimensions (EQ-5D-5L) score (adults/adolescents).

HRQoL will be evaluated at baseline, every 3 months, and at the end of the study).

The EQ-5D scale is composed of two main sections: in the first it is requested a subjective evaluation of five dimensions (mobility, selfcare, usual activity, pain discomfort, anxiety / depression), in the second an evaluation of the overall health status using a visual analogue scale (VAS) from 0 to 100. As for the first section, the original version of the scale (EQ-5D-3L) used a scoring system in 3 levels for each dimension, the most recent version a scoring system in 5 levels (1=no, 2=slight, 3=moderate, 4=severe, 5=extreme problems). An algorithm must be used to compute the synthetic index, commonly defined “EQ-5D Index Utility Score”, algorithm which assigns specific weights, defined “value set”, to each dimension of the health status. This value set is defined for a general population using techniques that are typical of the cost-utility analysis, following a protocol (EQ-VT) which has been developed by EuroQoL. This value set is Nation-specific. For Italy, the value set for the EQ-5D-5L is not yet available (validation is ongoing). However, a value set has been validated for the EQ-5D-3L (3). As recommended in the User’s Manual of the EQ-5D scale (4), it is possible to compute the so-called “crosswalk value set”, which allows to convert the value set of the 3-level scale (EQ-5D-3L) to the value set of the 5-level scale

(Eq-5d-5L) (5). In brief, using papers (3) and (5) it is possible to compute the Index Utility Score for Italy.

- Dose and frequency of concomitant medications taken to control pain (e.g., nonsteroidal anti-inflammatory drugs [NSAIDs], painkillers).

The concomitant medications flagged as “for pain treatment” in the eCRF during the study will be considered for this purpose.

- Joint health status of enrolled patients, based on Haemophilia Joint Health Score (HJHS) questionnaire (evaluated at baseline, at six months, and at the end of the study).

The HJHS is an instrument developed to measure joint health status and to identify early signs of joint disease in children. This tool assesses joints most commonly affected by bleeding (knees, ankles and elbows). Each of the 6 joints is assessed across 8 domains (swelling, duration of swelling, atrophy, crepitus, flexion loss, extension loss, pain and strength) and a Total Score is calculated as the sum of all joint domain scores. The instrument also includes a measure of Global Gait, which encompasses assessments of 4 skills: walking, climbing stairs, running and hopping on 1 leg.

- Body Mass Index (BMI) evaluated at baseline and every three months.
- Number of days away from school (patient) and/or work (patient and caregiver), and age of possible early retirement (caregiver) during the observation period, evaluated through administration of questions (evaluated at baseline, every month, and at the end of the study).
- Number of hospitalization days (patient) during the observation period evaluated through administration of questions (evaluated at baseline, every month, at the end of the study).
- Pain intensity measured using a Visual Analogue Scale (VAS) (evaluated at baseline, every month and at the end of the study).

The intensity of pain will be evaluated at baseline, every month and at the end of the study, as well as at each bleeding episode, by means of a 100 mm VAS and will be recorded through ePRO application. The left extreme of the horizontal line means “No pain = 0” while the right extreme means “Worst Pain Imaginable = 100”.

- To evaluate adherence to the treatment regimen: documented during planned visits according to source data (ePRO data) in electronic Case Report Forms (eCRF) by the investigator.

The adherence to the treatment regimen will be analyzed as proportion of “Yes” and “My therapeutic plan does not include any treatment in the last week” on the total of week reported via the ePRO. Missing data for some weeks will be treated as “No”. The total number of weeks will be derived as:

$$(End\ of\ study\ date - Baseline\ date + 1) / 7$$

- To describe the active vs. sedentary haemophiliac patients in terms of:
  - Severity of disease
  - Annualized bleeding rate (ABR)

The annualized bleeding rate will be derived as follows:

$$\frac{\text{total number of bleeds}}{\text{sum of the individual study's durations}}$$

where the individual study's duration will be given by

$$\text{end of study date} - \text{baseline date} + 1$$

- Pain and use of painkillers (as described above).
- Drug regimen adopted (as described above).
- HRQoL (as described above).
- Hospitalization/missed days at school (as described above).
- Joint Health Status (as described above).
- To describe severe vs moderate haemophiliac patients for the above mentioned items.

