Haemophilia A is associated with prolonged bleeding after trauma; spontaneous bleeding into joints, muscles, or soft tissues (*World Federation of Haemophilia 2013*), which can have a significant impact on patients' mobility and the HRQoL of both adult and adolescent patients (*Brown et al. 2009*).

Compared with control populations, people with Haemophilia have been shown to have moderate impairment of balance and mobility and reduced levels of physical activity (*Fearn et al. 2010*; *O'Donnell et al. 2014*). Improving mobility and safely increasing activity level in this population are important goals that will result in significant health and quality-of-life benefits (*von Mackensen et al. 2010*; *Czepa et al. 2013*). Ample scientific evidence and guidelines support the health promoting value of physical activity underlining the importance of assessing activity in adolescents and adults with Haemophilia. According to expert recommendations and the World Health Organization (WHO), adults should perform 10000 steps a day and accumulate at least 150 minutes of moderate-intensity physical activity throughout the week (*WHO 2010; Tudor-Locke C et al. 2011*).

Regular exercise is recommended to patients in order to promote strong muscles, develop balance, and improve fitness, which in return can contribute to healthier joints and diminish the occurrence of bleeds. However, physical activity likely to cause trauma, such as high contact and collision sports, should be avoided. (*Srivastava A et al. 2013*).

As expected, the degree of joint damage correlates with the level of activity. However, this parameter accounts for only a small fraction of the variability in the amount of activity performed by different people with Haemophilia (*Baumgardner et al. 2013*), which is not surprising as level of activity reflects both ability and motivation. Motivation (or lack thereof) is particularly important in people with Haemophilia who are at risk of bleeds with physical activity (*Broderick et al. 2012*), even when receiving standard therapies.

The amount and intensity of physical activity in children and adolescents with Haemophilia has previously been quantified using an accelerometer. However, no study has been performed in the adult Haemophilia population where the sequelae of different bleeds and consequent limitations on activity have been evaluated.

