#### **4.1.2 Evaluable population**

The evaluable population will consist of all enrolled patients with at least 6 valid months of physical activity evaluations during the study.

The patients with 6 valid months of physical activity will be defined by the presence of the two following conditions:

- an Extent of Exposure to the fitness tracker of at least 6 months (180 days) (see Section 4.3.1 for the definition of Exposure).

AND

- a compliance to the use of the fitness tracker of at least 50% in the period defined by the extent of exposure (see Section 4.3.2.1 for the definition of the compliance respect to the exposure).

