#### **4.1.3 Intention-to-treat Population (ITT)**

The Intention-To-Treat Population will consist of all enrolled patients who received the ePRO application and the fitness tracker.

All objectives will be evaluated both on the Evaluable population and on the ITT population. In case that the Evaluable population will consist of less the 50% (< 50%) of the ENR populations, only the primary endpoint and the secondary endpoint on the type of physical activity will be assessed on the Evaluable populations while all endpoints will be assessed on the ITT population.

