## **4.4 EFFICACY ANALYSIS**

#### **4.4.1 Co-primary Endpoints**

All the co-primary endpoints presented in Section 2.2.1, i.e.:

- active minutes:
  - heart zone minutes (overall, fat-burn minutes, cardio minutes, peak minutes)
  - active zone minutes (overall, lightly active minutes, fairly active minutes, very active minutes)
  - MVPA minutes
- METs
- number of steps

will be summarized at subject level as median per day (i.e. the median of each parameter will be calculated by using all the valid days collected during the observational period for each subject). Each parameter, derived as median per day at subject level, will be analyzed by means of descriptive statistics as described in Section 4. The 95% confidence interval for the mean will be also displayed.

The statistics will be shown overall and by age groups (12-17, 18-30 and 31-50). The comparison among the age groups will be performed by means of a one-way ANOVA or, if assumptions of normality is not confirmed (by a visual inspection: histogram and qq-plot), by means of a Kruskal-Wallis test.

Daily physical activity will also be summarized:

- by start of any newly approved drug for haemophilia (see Section 4.4.4 for subgroup definition).
- by COVID-19 period on the EVL population (see Section 4.4.4 for subgroup definition).
- by month through the entire observational period on the EVL to observe the impact of COVID-19.

Data will be summarized at subject level considering data collected in each period above-mentioned.

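### The SAP does not say how adult minutes per week are formed for WHO adherence and the active/sedentary label, and it sets no minimum number of valid days for that label in the ITT population or within periods

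*SAP*

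**What the plan says.** - **Adult rule (SAP 2.2.1).** A patient aged 18-50 is adherent with 150 fairly active minutes per week, or 75 very active minutes per week, or an equivalent mix in which one fairly active minute counts as half a very active one. Ages 12-17 need 60 MVPA minutes per day.
- **Source of the measures (SAP 2.2.1).** "The adherence to WHO guidelines will be derived considering the measures derived as described in Section 4.1". The same section says "A subgroup analysis will be done by severity of the disease (see Section 4.4.5 for subgroup definition", but the table of contents stops at 4.4.4.
- **Label (SAP 2.2.1).** An adherent patient "will be define as an “active patient”, otherwise as a “sedentary patient". SAP 4.4.4 refers back to 2.2.1 for this subgroup and adds no rule.
- **Daily data (SAP 2.2).** "Only data from days in which the fitness tracker was worn for at least 10 hours will be included in the statistical analysis".
- **Subject-level summary (SAP 4.4.1).** Each activity parameter "will be summarized at subject level as median per day", over all valid days. Amendment 1.1 gives robustness to scattered activity peaks and device errors as the reason.
- **Populations (SAP 4.1.2, 4.1.3).** Evaluable patients need a 180-day exposure and "a compliance to the use of the fitness tracker of at least 50% in the period defined by the extent of exposure". ITT patients need only to have received the app and the tracker. If fewer than half of the enrolled patients are Evaluable, only the primary endpoint and activity type are analysed on that population, "while all endpoints will be assessed on the ITT population".
- **Periods (SAP 4.4.2).** Adherence is recalculated by month and lockdown period on the Evaluable population, and by start of a newly approved drug without that restriction.
- **Protocol section 4.** Adults should "accumulate at least 150 minutes of moderate-intensity physical activity throughout the week".

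**The concern.** WHO adherence is a named secondary endpoint with a Clopper-Pearson interval. Its result also becomes the active/sedentary variable, which carries a whole secondary objective: severity, bleeding rate, pain and painkillers, drug regimen, HRQoL, hospitalisation and missed school days, and joint status.

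The weekly quantity behind it is undefined in the supplied text, so two programmers could form different groups from the same data. The obvious repair, reading 4.1 as 4.4.1, reaches a statistic chosen to discount scattered peaks, whereas a weekly total has to count them. The catch-all sedentary category also takes in patients about whom the tracker says very little. Under some constructions the split would partly reflect tracker wear instead of activity.

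**Working it through.** **1. Search for a weekly rule.** SAP 2.2 defines the daily components (fairly active, very active, MVPA) but no weekly aggregation. SAP 4.4.1 gives a median per valid day. In SAP 4.4.2, the week/month remapping covers ePRO endpoints, and the only x 7 formula is a rate of activity counts, not minutes. The WHO paragraph there adds an interval and breakdowns, but no derivation. SAP 4.4.4 points back to 2.2.1.

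**2. The plan's own thresholds.** They agree with each other: 150 x 0.5 = 75. The three alternatives also reduce to one. With F fairly active and V very active minutes per week, 0.5F + V >= 75 is the same as F + 2V >= 150, and F >= 150 or V >= 75 alone already implies it. A check of all F from 0 to 300 and V from 0 to 150 found no exception.

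**3. If 4.4.1 is meant and its median is scaled to a week (fully worn week, moderate minutes).**

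| Pattern | Weekly total | 7 x median | 7 x mean |
|---|---|---|---|
| 60 min on 3 days | 180 (adherent) | 0 | 180 |
| 25 min on 4 days | 100 (not adherent) | 175 | 100 |
| 26 min on 7 days | 182 (adherent) | 182 | 182 |

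The first two labels reverse; the third shows that the median is right when activity is even. The mixed rule is ambiguous as well. Take 40 moderate minutes on three days and 20 vigorous minutes on three others, a moderate-equivalent total of 120 + 2 x 60 = 240. This scores 0 if each median is taken separately, and 7 x 40 = 280 if the median is taken of the daily combination.

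**4. If an unscaled sum over valid days is meant.** A true total T passes, on average, only when the valid-day fraction is at least 150/T: 150/180 = 83%, 150/200 = 75%, 150/300 = 50%. At the Evaluable limit of 50% valid days, the daily average needed rises from 150/7 = 21.4 to 150/3.5 = 42.9 minutes.

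**5. If only complete weeks count.** With valid days scattered at random (an assumption), the share of complete weeks is p^7: 48%, 13% and 0.8% at p = 0.90, 0.75 and 0.50. That is about 25, 7 and 0.4 weeks out of 52.

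**6. Minimum data.**
- Evaluable, whole study: 50% of 180 = 90 valid days at least, so up to 90 non-valid days in such a span.
- Lockdown periods, counting both end dates: 1 March to 4 May 2020 is 65 days, and 13 October to 31 December 2020 is 80. Both are shorter than 90, so an Evaluable patient may have few or no valid days in either.
- ITT: no minimum. On one valid day, the adult with 60 minutes on three days a week scores 7 x 60 = 420 (chance 3/7) or 0 (chance 4/7), whether the mean or the median is scaled.
- With n valid days, each independently active with probability 3/7 (an assumption), 7 x mean labels this adherent adult active when 420k/n >= 150, where k is the number of active days. The binomial probability is 43% for n = 1, 64% for n = 7 and 90% for n = 90.
- ITT-only fallback: fewer than 50% of 107 is 53 or fewer Evaluable patients, if all 107 count as enrolled.

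**The case against.** **The SAP never says that 7 x median is used for adherence.** This is correct. A reader might infer that adult adherence will be computed that way and will be wrong. The documents do not support that: it needs two assumptions, that 4.1 means 4.4.1 and that per week means seven times the daily median. Section 2.2, which defines the component minutes, is an equally plausible target. The misclassification is conditional; the missing definition is not.

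**Low wear is partly handled.** All objectives are run on both populations, so the Evaluable result checks the ITT result unless the 50% fallback applies. Month and lockdown summaries are restricted to Evaluable patients. Under SAP 4.7, a patient with no valid day could be counted as missing. All of this stands. It does not cover patients with few valid days in ITT or within a period. For its bleeding analyses, SAP 4.4.2 states what to do when only one valid day is available; it has no counterpart here.

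**The adolescent rule.** A reader might infer that ages 12-17 are undefined too. If 4.4.1 is the intended source, they are not: MVPA minutes are listed there and summarised as the median per valid day. Only confirmation is needed.

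**7 x mean is also a choice.** Also true. It describes an average week: 26 weeks at 310 minutes and 26 at 0 average 155, adherent, although half the weeks miss the target. A rule based on the proportion of weeks meeting the target would answer a different question.

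**Attachments.** The wear-time report and mock shells may contain a rule. If so, the SAP should cite it.

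**Conclusion.** The point holds in conditional form. As supplied, the SAP leaves the adult weekly measure undefined, and its cross-reference leads to analysis populations. Of the candidate constructions, a scaled median can reverse labels in both directions and an unscaled sum falls with non-wear; each is right only in special cases (even daily activity, complete wear). Separately, the sedentary label has no minimum data in ITT or within any period. The Evaluable floor of 90 valid days limits this only for whole-study Evaluable results.

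The examples are constructed weeks, and the probabilities assume independent or randomly missing days. The documents give no activity distribution, so neither the number of misclassified patients nor the bias in any active/sedentary comparison can be stated. The analyses concerned are exploratory and largely descriptive. This is an inexpensive improvement to make before database lock, not a threat to the primary objective. Confidence is high for the missing definition and the missing minimum; how much misclassification results depends on what the programmers would actually do.

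**What to change.** 1. Correct the references to Sections 4.1 and 4.4.5 in SAP 2.2.1.
2. Ages 18-50: define adherence as 7 x mean over valid days of (fairly active + 2 x very active minutes) >= 150, within each analysis period. Describe it as adherence in an average week, and show the median-based result as a sensitivity analysis.
3. Ages 12-17: confirm that the 4.4.1 daily summary of MVPA minutes applies. Changing it to the mean, to match the adult rule, is optional.
4. Report patients below a prespecified minimum of valid days as not classifiable, not as sedentary.
   - Per period: at least 50% of the days on which the patient was under observation in that period. The calendar length of a lockdown is the wrong denominator because enrolment was staggered. A patient who consented on 10 April 2020 has only 25 days in the first lockdown, so a threshold of 33 of 65 could not be met even with perfect wear.
   - Overall in ITT: a fixed minimum count chosen before database lock. The compliance percentage of 4.3.2.1 cannot serve, because a single valid day gives an exposure of 1 day and compliance of 100%.

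**Cost.** SAP wording and a small programming change; no new data. The mean is more sensitive to outlier days, which the median-based analysis would show. 7 x mean assumes that unworn days resemble worn days and hides week-to-week variation. Some patients leave the active/sedentary comparison, and their number should be reported.
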